## 7.7 Statistical Analyses Methodology

Statistical analyses will be performed using SAS software Version 9.2 or later. Continuous variables will be summarized using descriptive statistics, including but not limited to the mean, the standard deviation, median, minimum value, and maximum value. Categorical variables will be summarized using frequency counts and percentages. All data collected across the 4 treatment groups throughout the study will be listed in data listings.

All statistical tests will be 2-sided and performed using a 5% significance level, leading to 95% (2-sided) CIs. As the primary efficacy endpoint is analyzed at the interim analysis and at the end of the study, multiplicity will be addressed by using a combination test to combine the results (see Section 7.7.1). A hierarchical method will be employed to address any multiplicity arising from the analysis of the key secondary endpoint. In other words, the formal analysis of this endpoint will be performed only if a statistically significant result is obtained from the combination test analysis of the primary endpoint. All analyses performed on the other secondary endpoints are for exploratory purposes only; therefore, no further multiplicity adjustment is required.

The combined analysis of patients from Parts 1 and 2 rests on the assumption that patients recruited in each part of the study will belong to the same overall patient population. To check this assumption, data related to the baseline characteristics (for all 4 treatment groups) will be repeated for Part 1 and Part 2. If any notable differences are observed, then the combined analysis of Parts 1 and 2 will need to be interpreted with caution and further exploratory analysis will need to be conducted to investigate the possible causes.

The assumption of a consistent treatment effect across Parts 1 and 2 will be investigated by repeating the primary and key secondary efficacy analyses (for the optimal recAP dose and placebo treatment groups) for Part 1 and Part 2. Again, any notable differences will lead to the combined analysis of Parts 1 and 2 being interpreted with caution and further exploratory analyses conducted to investigate the possible causes.

Further details of the statistical analyses, methods, and data conventions will be described in the SAP.

### **7.7.1 Analysis of Primary Efficacy Endpoint**

The primary efficacy endpoint is the area under the time-corrected endogenous creatinine clearance curve from Day 1 to Day 7, i.e.,  $AUC_{1-7}$ .

Area under the time-corrected endogenous creatinine clearance curve from Day 1 to Day 7 will be summarized using descriptive statistics and analyzed using an analysis of variance (ANOVA) with treatment and site as explanatory variables. The analysis will be performed separately for Parts 1 and 2: for Part 1,  $AUC_{1-7}$  will be compared between the 3 recAP doses and placebo. This analysis will be considered in conjunction with the safety data to determine

the optimal recAP dose for use in Part 2. For Part 2, the optimal recAP dose will be compared with placebo. Confirmatory testing of the single hypothesis comparing optimal dose with placebo will be based on a closed-testing procedure. This hypothesis will be rejected at level  $\alpha$  if it and all intersection hypotheses involving it are all rejected at local level  $\alpha$ . The testing strategy used to combine results from Parts 1 and 2 will be a combination test based on the inverse normal method, with the test statistic of the combination test calculated as (Bauer and Köhne 1994):

$$\sqrt{\frac{n_1}{n}} \Phi^{-1}(1 - p_1) + \sqrt{\frac{n_2}{n}} \Phi^{-1}(1 - p_2)$$

where  $n_1$  and  $n_2$  are the sample sizes per group in Parts 1 and 2, respectively,  $n = n_1 + n_2$ ,  $\Phi$  refers to the standard normal distribution, and  $p_1$  and  $p_2$  are the p-values from Parts 1 and 2, respectively. For the single hypothesis,  $p_1$  is the unadjusted p-value to compare optimal dose with placebo in Part 1. For the intersection hypotheses,  $p_1$  is the Dunnett-adjusted p-value in Part 1, and  $p_2$  is the unadjusted p-value to compare optimal dose with placebo in Part 2 for all hypotheses.

The difference in least squares means between the treatment groups will also be presented along with the associated 95% CI.

The underlying assumptions for ANOVA (normality and homogeneity of variance of the studentized residuals) will be investigated for Part 1 by examining a normal probability plot of the residuals and a plot of the fitted values against the residuals. Should there be a strong indication that these assumptions are not satisfied, a corresponding non-parametric analysis will be conducted to calculate the p-values for Parts 1 and 2 (i.e., using ANOVA with the rank-transformed values of  $AUC_{1-7}$  as the outcome variable and treatment and site as explanatory variables).

In addition to the above, the summarization using descriptive statistics will be repeated for all 4 treatment groups for the patients randomly assigned prior to Part 2.

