### **6.2.3 Efficacy Assessments**

The following assessments will be considered as efficacy measurements.

- Urine volume, urinary creatinine, and the average of two serum creatinine measurements will be used for the calculation of time-corrected endogenous creatinine clearance at all visits from baseline to Day 7, and will be calculated by the central laboratory. The measurements from Day 1 to Day 7, inclusive, will be used to calculate the primary endpoint. Only if reliable urine collection is possible, urine will be collected on Days 14, 21, and 28 for time-corrected endogenous creatinine clearance calculation (i.e., patient is in the ICU or intermediate care unit or hospital). If reliable urine collection is not possible, one serum creatinine sample still needs to be taken for calculating eGFR.

- Urine volume collection in a  $6 \pm 1$  hour collection period at baseline and at all visits from Day 1 to Day 28, but only required if reliable urine collection is possible (i.e., patient is in the ICU or intermediate care unit or hospital)
- BUN clearance at all visits from Day 1 to Day 7.
- Urinary urea at baseline and at all visits from Day 1 to Day 28, only if reliable urine collection is possible (i.e., patient is in the ICU or intermediate care unit or hospital)
- Fractional excretion of sodium at all visits from baseline to Day 7
- Fractional excretion of urea at all visits from baseline to Day 7
- Proteinuria at baseline and at all visits from Day 1 to Day 90
- Tubular injury biomarkers, KIM-1, IL-18 and GST-alpha, in urine at baseline and at all visits from Day 1 to Day 28
- Serum creatinine at baseline and at all visits from Day 1 to Day 90
- Serum BUN at baseline and at all visits from Day 1 to Day 28.
- Systemic inflammatory serum biomarkers, e.g., IL-6, CRP, LBP, at baseline and at all visits from Day 1 to Day 28
- RRT incidence, considered as the key secondary endpoint, during the study period Day 1 to Day 28
- RRT duration, during the study period Day 1 to Day 28
- Incidence of dialysis dependency on Day 60 and Day 90
- SOFA score results at baseline, at all visits from Day 1 to Day 28 (when patient is in the ICU or intermediate care unit), and on the day of ICU or intermediate care unit discharge if discharged on a non-visit day. Note that platelets, bilirubin, creatinine and urine output are required to obtain a SOFA score.
- Quality of life, EQ-5D questionnaire at baseline, at ICU or intermediate care unit discharge, and Day 90

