Please note that any patients who do not receive any dose of study drug will be excluded from the safety and PP analyses, and therefore do not need to be considered in the [Table 4-1](#). Dose windows were constructed in line with the weight ranges and corresponding pre-calculating volumes displayed in [Table 15-3](#). See [Section 15.3](#) for full justification of these windows.

Statistical Analysis

All statistical tests will be two-sided and performed using a 5% significance level, displaying 95% two-sided confidence intervals (CIs), unless specifically stated otherwise. As the primary efficacy endpoint is analyzed at the interim analysis and at the end of the study, multiplicity will be addressed by using a combination test to combine the results (see [Section 8.1.1](#)). A hierarchical method will be employed to address any multiplicity arising from the analysis of the key secondary endpoint. In other words, the formal analysis of this endpoint will be performed only if a statistically significant result is obtained from the combination test analysis of the primary endpoint. All analyses performed on the other secondary endpoints are for exploratory purposes only; therefore, no further multiplicity adjustment is required.

All analyses will be undertaken using SAS[®] Version 9.2 (SAS Institute, Inc, Cary, North Carolina) or later.

Weight

Body weight (in kg or lb) will be measured or estimated at screening. Weight will be displayed in kg and derived from lb as:

$$Weight[kg] = \frac{Weight[lb]}{2.2046}$$

Temperature

Temperature (in °C or °F) will be measured from Day 1 – Day 28. Temperature will be displayed in °C and derived from °F as:

$$Temperature[°C] = \frac{Temperature[°F] - 32}{1.8}$$

Laboratory Data

For laboratory data that are recorded as values of '<x' and '>x' where x is any numeric value, the numeric part after the '>' and '<' (i.e. x) will be used for summarizing and in graphical presentations. In addition the numeric part will be used in the derivation of the quartile-based subgroup definitions.

In the tables where serum creatinine or CRP data are presented, if a subject has missing baseline central laboratory measured serum creatinine or CRP values, but has available baseline local laboratory measured values then the local laboratory values will be used to

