8.1.1. Primary Analysis

The primary efficacy analysis will be an analysis of variance (ANOVA) of the area under the time-corrected endogenous creatinine clearance curve from Day 1 to Day 7 with treatment and site as explanatory variables.

For all patients recruited up to the interim analysis, the primary efficacy analysis will be conducted for the ITT Combined Set at the interim analysis (which is identical to the ITT Part 1 Interim set at the time of the interim analysis) where AUC_{1-7} will be compared between the 3 active treatment groups and placebo. This analysis will be considered in conjunction with the safety data to determine the optimal recAP dose for use in Part 2.

The primary efficacy analysis will be conducted for the ITT Part 2 Set, PP Day 1 – 7 Part 1 and PP Day 1 – 7 Part 2 Set where AUC_{1-7} will be compared between the optimal recAP dose and placebo (for the PP Day 1 -7 Combined Set, each dose of recAP will be compared to Placebo). Also, all doses combined will be compared to Placebo.

Confirmatory testing of the single hypothesis comparing optimal dose with placebo will be based on a closed-testing procedure. This hypothesis will be rejected at the 5% significant level if it and all intersection hypotheses involving it are all rejected at the 5% significance level. The testing strategy used to combine results from Parts 1 and 2 will be a combination test based on the inverse normal method, with the test statistic of the combination test calculated as ([Bauer and Köhne 1994](#)):

$$\sqrt{\frac{n_1}{n}} \Phi^{-1}(1 - p_1) + \sqrt{\frac{n_2}{n}} \Phi^{-1}(1 - p_2)$$

where n_1 and n_2 are the sample sizes per group in interim analysis at Part 1 and in Part 2, respectively, $n = n_1 + n_2$, Φ refers to the standard normal distribution, and p_1 and p_2 are the one-sided p-values from interim analysis at Part 1 and from Part 2, respectively. For the intersection hypotheses, p_1 is the Dunnett adjusted one-sided p-value in Part 1 (for the optimal dose selected), and p_2 is the one-sided unadjusted p-value to compare optimal dose with placebo in Part 2 for all hypotheses.

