8.1.3. Assumption Testing

The underlying assumptions for ANOVA (normality and homogeneity of variance of the studentized residuals) will be investigated at the Part 1 interim analysis and at the Part 2 analysis by examining a normal probability plot of the residuals and a plot of the fitted values against the residuals. These results will be presented as a SAS[®] output.

Should there be a strong indication that these assumptions are not satisfied, a corresponding non-parametric analysis will be conducted to calculate the p-values for interim analysis at Part 1 and at Part 2 (i.e., using ANOVA with the rank-transformed values of AUC₁₋₇ as the outcome variable and treatment and site as explanatory variables).

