8.1.4. Sensitivity Analyses

The interim analysis was conducted on non-adjudicated data, so will be repeated using only the data deemed acceptable by the adjudication committee, therefore a sensitivity analysis will be performed on the primary endpoint using adjudicated Part 1 data.

In order to investigate the effect of imputing the missing data with LOCF, a sensitivity analysis will be conducted on the primary efficacy endpoint. The ANOVA analysis will be performed as described in [Section 8.1.1](#) but excluding any patients that died prior to Day 8 of the study. The descriptive statistics for the primary endpoint will also be repeated for this sensitivity analysis.

In addition, the ANOVA analysis (as described in [Section 8.1.1](#)) will be repeated including as additional covariates the baseline serum creatinine results and the baseline APACHE II score for the ITT Combined Set for the optimal recAP dose and Placebo. If the analysis does not converge, APACHE score will be categorized into two categories (< 25, ≥25).

Finally, the area under the time-corrected endogenous creatinine clearance curve from Day 5 to Day 7 (AUC₅₋₇) will be derived and analyzed with an ANOVA as described in [Section 8.1.1](#) to determine if the AUC₅₋₇ is a predictor of treatment effect.

AUC₅₋₇ is calculated as the average of the standardized endogenous creatinine clearance values over the 3 days. Specifically, denoting C_i as the standardized endogenous creatinine clearance on Day i , AUC₅₋₇ is defined as:

$$AUC_{5-7} = \frac{1}{3} \sum_{k=5}^7 C_i$$

Any missing C_i values will be handled by linear interpolation where possible, otherwise they will be imputed by last observation carried forward (LOCF). When there are no preceding post-baseline measurements to use, the baseline measurement from Day 0 (i.e., prior to treatment) will be carried forward. If there are missing values the values imputed for deriving AUC_{1-7} will be used to derive AUC_{5-7} .

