8.1.5. Supportive Analysis for the Primary Efficacy Endpoint

Due to the high variability of the creatinine clearance, the change from baseline in serum creatinine at Day 7 will be analyzed using an ANOVA with baseline serum creatinine, treatment (optimal recAP dose and placebo) and site as explanatory variables. The analysis will be run on the ITT Combined Set. If there is more than one serum creatinine result collected at Day 7, the average at Day 7 will be used to derive the change from baseline.

Additionally the primary endpoint analysis will be repeated with the following variables as additional factors within the ANOVA model for the ITT Combined Set (for the optimal recAP dose and placebo):

- Baseline biomarkers for kidney function:
 - Fractional excretion of sodium (<1%, ≥1 % - ≤2%, >2%).
 - Fractional excretion of urea (<35%, ≥35%).
- Baseline AKIN stage (stage 1, stage 2 and stage 3).
- Microbial infection. The following are the five possible outcomes:
 1. Gram positive
 2. Gram negative
 3. Mix gram positive/gram negative
 4. Other (e.g. fungal)
 5. Unknown.

If a blood culture is available this is leading. (Note that if a staphylococcus epidermis is the outcome this is a contamination and should be ignored). If no blood culture is available, the culture from the site for which the patient was hospitalized (index indication) is leading e.g. patient hospitalized for lung infection, with positive sputum and positive urine culture: sputum is then leading.

- Baseline urinary biomarkers for proximal tubular cell damage:

- KIM-1 (<Q1, ≥Q1 - <Q2, ≥Q2 - <Q3, ≥Q3).
- IL-18 (<Q1, ≥Q1 - <Q2, ≥Q2 - <Q3, ≥Q3).
- GST-alpha (<Q1, ≥Q1 - <Q2, ≥Q2 - <Q3, ≥Q3).

For GST-alpha, two different kits were used in the testing of GST-alpha therefore quartiles will be calculated separately for each kit and then for each subject, their baseline value will be compared against the quartile for the kit that was used to assess their GST-alpha baseline result. The resulting assigned quartile categories will then be combined together for subgroup summaries regardless of which kit was used.

- Baseline biomarkers for systemic inflammation:
 - IL-6 (<Q1, ≥Q1 - <Q2, ≥Q2 - <Q3, ≥Q3).
 - CRP (<Q1, ≥Q1 - <Q2, ≥Q2 - <Q3, ≥Q3).
 - LBP (<Q1, ≥Q1 - <Q2, ≥Q2 - <Q3, ≥Q3).
- Baseline eGFR by CKD-EPI formula (<Q1, ≥Q1 - <Q2, ≥Q2 - <Q3, ≥Q3).
- Time from first diagnosis of SA-AKI to start of recAP treatment (0 to <6 hours, 6 to <12 hours, 12 to <18 hours, 18 to <24 hours, ≥24 hours).

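### Baseline serum creatinine enters only a sensitivity model; putting it in the Part 2 primary model would add modest power for one degree of freedom

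*Protocol*

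**What the plan says.** Protocol 7.7.1 states that the primary endpoint is "analyzed using an analysis of variance (ANOVA) with treatment and site as explanatory variables". SAP 8.1.1 specifies the same model for the "endogenous creatinine clearance curve from Day 1 to Day 7 with treatment and site as explanatory variables". One-sided p-values from this model, one per part, feed the inverse-normal combination test.

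Baseline renal function is measured. Protocol 6.2.3 lists "Serum creatinine at baseline and at all visits from Day 1 to Day 90" among the efficacy assessments. SAP 8.1.4 uses it: the ANOVA is to be "repeated including as additional covariates the baseline serum creatinine results and the baseline APACHE II score for the ITT Combined Set", for the selected dose and placebo. SAP 8.1.5 adds a supportive model with baseline serum creatinine as an explanatory variable, but for a different outcome: "Due to the high variability of the creatinine clearance, the change from baseline in serum creatinine at Day 7 will be analyzed".

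Three other passages bear on any change:

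- SAP 8.1.4 reports that "The interim analysis was conducted on non-adjudicated data".
- The local-laboratory fallback in SAP 4 (Laboratory Data) is written for tables, and applies "if a subject has missing baseline central laboratory measured serum creatinine or CRP values, but has available baseline local laboratory measured values".
- If the ANOVA assumptions fail, SAP 8.1.3 says "a corresponding non-parametric analysis will be conducted to calculate the p-values for interim analysis at Part 1 and at Part 2", again with treatment and site only.

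Neither document gives the correlation between baseline serum creatinine and AUC1-7, or a reason for leaving it out of the primary model.

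**The concern.** A prognostic covariate that is fixed before unblinding reduces residual variance and leaves the type I error alone. Here the covariate is already collected, already programmed for a secondary fit, and attached to an outcome that the SAP itself calls highly variable. Patients enter at AKIN stage 1 or above and randomisation is stratified by site only, so the design does nothing to balance baseline renal severity.

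The planned adjusted analysis uses the ITT Combined Set. It supplies neither stage p-value and cannot alter the decision. What is at stake is power on the primary test and, through the hierarchy, whether RRT incidence is tested formally at all.

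**Working it through.** **Inputs from the documents** (Protocol 7.4, 7.7.1, 7.7.6; SAP 4.1, 8.1.1): n1 = 30 in each of four arms; n2 = 85 in each of two arms; SD 49 mL/min; placebo mean 60; active means 60 to 79; one-sided 2.5%; Dunnett-adjusted p1 for the intersection hypotheses; stop if all three one-sided p-values exceed 0.8.

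**Assumed:** the linear correlation ρ between baseline serum creatinine and AUC1-7, from 0 to 0.5. SD 49 is taken as unadjusted. Site is ignored at first.

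**Statistic:** √(30/115)·Φ⁻¹(1 − p1) + √(85/115)·Φ⁻¹(1 − p2). The squared weights are 30/115 = 26% and 85/115 = 74%.

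**Step 1, reproduce the plan.** With 100,000 runs per scenario and the best Part 1 mean selected:

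- The scenarios stated at 79% to 86% give 79.3% to 85.6%.
- For the scenarios stated at 66% to 67%, the low and medium means are not listed. Medium at 69.5 with low at 60 or 69.5 gives 67.0% and 65.4%. With both at 60 the result is about 69%, outside the stated range, so that case is not used.
- Type I error is 2.45% to 2.50% (two seeds of 200,000 runs), against the stated 2.4%.

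**Step 2, covariate in Part 2 only.** The baseline value is simulated with correlation ρ and the ANCOVA is fitted; p1 is unchanged. Power (%):

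| Means: placebo, low, medium, high | None | ρ = 0 | 0.2 | 0.3 | 0.4 | 0.5 |
|---|---|---|---|---|---|---|
| 60, 69.5, 79, 79 | 79.3 | 79.2 | 80.2 | 81.5 | 83.4 | 86.0 |
| 60, 79, 79, 79 | 85.6 | 85.4 | 86.4 | 87.6 | 89.4 | 91.6 |
| 60, 60, 69.5, 79 | 67.0 | 66.8 | 68.0 | 69.4 | 71.3 | 74.2 |
| 60, 69.5, 69.5, 79 | 65.4 | 65.3 | 66.3 | 67.7 | 69.9 | 72.8 |

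Subtracting the first column, the change is −0.1 to −0.2 points at ρ = 0, +0.8 to +1.0 at 0.2, +2.0 to +2.4 at 0.3, +3.8 to +4.5 at 0.4 and +6.0 to +7.4 at 0.5. Type I error with the covariate (ρ = 0.3) is 2.46% to 2.50%.

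**Step 3, cross-check by formula.** The adjusted SD is 49·√(1 − ρ²), which is 48.0, 46.7, 44.9 and 42.4 for ρ = 0.2, 0.3, 0.4 and 0.5. The equivalent Part 2 size is 85/(1 − ρ²), which is 88.5, 93.4, 101.2 and 113.3 per arm. Putting these SDs into the two-stage simulation, with one degree of freedom fewer, gives 80.5%, 81.6%, 83.6% and 86.0% in the first scenario. This agrees with the table.

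**Step 4, cost if the covariate is useless.** The variance factor is 1 + 1/(168 − 2) = 1.006. Part 2 power taken alone, for a difference of 19, falls from 71.0% to 70.7%. With 90 residual degrees of freedom it falls from 70.6% to 70.1%.

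**Step 5, site fitted.** With site as a fixed effect and 50 or 100 equally likely sites (12,000 runs), the change in combined power across the four scenarios is −0.2 to −0.4 points at ρ = 0, +0.6 to +0.9 at 0.2, +2.2 to +2.8 at 0.3 and +7.0 to +8.2 at 0.5. The gain survives, but absolute power is lower with or without the covariate. Assuming skewed accrual over 100 sites, Part 2 power taken alone is 62% to 63%, against about 70% without site.

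**Step 6, covariate in both parts.** This is available only if the interim has not been run. Power in the first two scenarios would be 80.7% to 86.7% at ρ = 0.2, 82.6% to 88.4% at 0.3 and 88.9% to 93.6% at 0.5. In the last two it would be 66.8% to 68.5%, 69.1% to 70.9% and 77.1% to 78.9%.

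**The case against.** **The plan meets its own power target without the covariate.** True. Nothing here invalidates the planned test.

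**ρ is unknown and may be low.** This stands. Protocol Appendix 5 describes creatinine-based GFR estimates as unreliable when renal function is not in steady state. Patients can enter on urine output alone. The analysed baseline value is not corrected for fluid. Clearance has serum creatinine in its denominator, so the relation need not be linear. Misfit would cost efficiency but not validity. A correlation of 0.2 or less would make the gain about a point at most.

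**Site costs more than the covariate recovers.** Under the accrual assumed above, about 100 site terms cost more power than the covariate regains at ρ = 0.3. That is a separate issue and does not remove the gain. It does mean that the table's percentages should be read as differences, not as achievable power.

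**Changing the primary model after the interim is more than editing.** Protocol 7.7.1 defines the test, so an amendment under Protocol 10.2.1 would be needed, and the people making the change must be blinded. This is fair. However, the SAP change history shows rules for the primary analysis still being revised in September 2017. The two stages also already differ: p1 uses non-adjudicated clearance data and Part 2 uses adjudicated data.

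**The adjusted result will be reported anyway.** It will, but only as sensitivity and supportive analyses that leave p2 unchanged.

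**Conclusion.** The point holds as an efficiency improvement. The confirmatory p-values come from a model with treatment and site only, and the one AUC1-7 model that adds baseline serum creatinine as a continuous covariate cannot affect the decision. Moving it into the Part 2 model adds about 1 point of power if ρ is 0.2, about 2 if 0.3, about 4 if 0.4 and 6 to 7 if 0.5. If ρ is 0 it loses less than half a point.

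The size rests on the assumed ρ, on SD 49 being the unadjusted value, and on the interim having been completed. Confidence in the direction is high; confidence in the amount is moderate. Any benefit to dose selection, or to chance imbalance in Part 1, exists only if the interim is still to come.

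**What to change.** Before unblinding, and by staff who have not seen Part 2 results by arm:

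1. In Protocol 7.7.1 and SAP 8.1.1, make the primary Part 2 model an ANCOVA of AUC1-7 with treatment, site and baseline serum creatinine, and take p2 from it.
2. Leave p1 and the weights as they are; the inverse-normal test needs only a valid p-value from each stage. If the interim has not in fact been run, use the same model for p1.
3. Keep the unadjusted ANOVA as the sensitivity analysis (SAP 8.1.4). It also lets the planned Part 1 versus Part 2 consistency check use one model for both parts.
4. Extend the local-laboratory fallback in SAP 4 to this model. Add a rule that keeps patients with neither value in the ITT test, for example by imputing the overall baseline mean without regard to arm.
5. Carry the covariate into the rank-based fallback (Protocol 7.7.1, SAP 8.1.3), and state whether it is ranked.

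APACHE II can stay in the sensitivity model; no gain was computed for it. A pooled, blinded estimate of ρ would show in advance how much the change is worth.

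The cost is a protocol amendment and SAP revision, a missing-baseline rule and one degree of freedom in Part 2. No new data are needed.
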